MRC Integrative
Epidemiology
Unit

University of
BRISTOL

School of Psychological Science
[name]
[name]
United Kingdom

[contact]
www.bristol.ac.uk

STUDY PROTOCOL

INCREASING THE RELATIVE AVAILABILITY OF ALCOHOL-FREE DRINK OPTIONS IN BARS AND PUBLIC HOUSES: A FIELD STUDY

[name], [name], [name], [name], [name], [name], [name], [name], [name], [name], [name], [name], [name], [name]

Background

Interventions that alter the availability of healthier and less healthy products, within the environments from which they are purchased or consumed, can facilitate healthier consumption (Allan *et al.*, 2017; Grech and Allman-Farinelli, 2015; Pechey *et al.*, 2019; Hollands *et al.*, 2019). These can be classified as Availability x Product interventions, based on the Typology of Interventions in Proximal Physical Micro-Environments (TIPPE) (Hollands *et al.*, 2017).

A Cochrane review of the impact of reducing the availability of less healthy products on their selection and consumption, reported large effects on selection and a moderate effect on consumption (Hollands *et al.*, 2019). However, concerns regarding study quality and sample size were identified and uncertainty for the reliability of these findings remains. In addition, the review only identified studies related to food products and the effectiveness of availability interventions for reducing alcohol consumption is unknown.

A recent online study found that the odds of selecting an alcohol-free drink were 71% higher when the proportion of alcohol-free drinks compared to alcoholic drink options increased from half to three-quarters, and were 37% lower when they decreased to one-quarter (Blackwell *et al.*, 2019). A subsequent online study indicated that increasing the proportion of non-alcoholic drinks available – from 25% to 50% or 75% – reduces alcohol selection and purchasing (Clarke *et al.*, 2022). While both of these studies provide initial support for availability interventions in relation to alcohol products, replication in real world environment with behavioural outcomes is required.

The development of low and alcohol-free drink options is encouraged as part of a broader range of evidence-based strategies to reduce alcohol-related harm (Anderson *et al.*, 2013). Alcohol-free drink options are often given secondary importance in restaurants and bars (e.g., listed at the back of a menu or stored in a low-level fridge). Ubiquitous alcohol marketing within drinking environments, as well as stigma around drinking alcohol-free drinks,

discourages alcohol-free drink selection and consumption (HardcastleO'connor and Breen, 2019; Davies Emma, 2018; Club Soda, 2016).

However, the market for low and alcohol-free drink alternatives is growing (The Morning Advertiser, 2019). Widening the choice available for consumers and increasing alcohol-free drink exposure could encourage their selection and shift social norms (RenoCialdini and Kallgren, 1993; Zajonc, 2001). Increasing the availability of alcohol-free alternatives provides an opportunity for licensed venues to take positive action to address licensing objectives regarding public safety and crime and disorder, broaden their offer to customers and maintain revenue (Club Soda, 2016; Licensing Act 2003 C.17). Additionally, the UK Government has pledged to increase the availability of alcohol-free and low-alcohol products by 2025 (Department of Health and Social Care, 2021), although details on what this would involve have yet to be published.

Evidence of the impact of increasing the availability of alcohol-free drink options on alcoholic and alcohol-free drink selection and consumption is required to support policy decisions in this area.

Study Aim and Hypotheses

The aim of this study is to estimate the impact of increasing the proportion (i.e., the relative availability) of draught alcohol-free beer on alcohol consumption in bars and public houses.

Hypothesis: Replacing one draught alcoholic beer with one draught alcohol-free beer lowers the volume of draught alcoholic beer sold in licensed premises.

Hypothesis: Replacing one draught alcoholic beer with one draught alcohol-free beer does not reduce the revenue from all drinks sold in licensed premises.

Study Design

A minimum of 12 and up to 16 sites (bars and public houses) in the UK will be recruited to take part in this randomised four-period crossover trial. All participating sites will perform two intervention periods (A) and two control periods (B) in a random order. A minimum of three and up to four sites will be randomised to each of four possible orders: 1) BABA; 2) BAAB; 3) ABBA; or 4) ABAB. Each period will last two weeks and therefore each site will be monitored for eight weeks in total. During the intervention condition, sites will remove one draught alcoholic beer and replace it with one draught alcohol-free beer. During the control condition, sites will have no alcohol-free beer on draught (i.e., usual practice).

Intervention

Sites will remove one draught alcoholic beer (i.e., alcoholic lager or ale) and replace it with one draught alcohol-free beer (i.e., alcohol-free lager or ale). Sites will be able to choose which draught alcoholic beer to remove and which draught alcohol-free beer to replace it with. Sites will be encouraged to replace this like-for-like (i.e., replace a draught alcoholic lager with a draught non-alcoholic lager). However, if sites have strong motivations for not wanting to replace like-for-like (i.e., sites want to replace an alcoholic ale with an alcohol-free lager) this will be permitted. All replacements throughout the study will be kept consistent, for example if an alcoholic lager is replaced by an alcohol-free lager, then this

same replacement must be used throughout the study (i.e., using the same brand and type).

The beer type (lager or ale) for both the removed alcoholic beer and the replacement alcohol-free beer will be recorded for each site and described descriptively. The brand also be recorded for the alcohol-free replacement and described descriptively.

As part of the intervention, sites will be encouraged to advertise the new draught beer in the same way as it would with any other new product (tap badges, signs behind the bar and information on menus and any apps). These practices will be recorded but not controlled.

Within the TIPPME intervention typology for changing environments to change behaviour (Hollands et al., 2017), the type of intervention proposed here is Availability and is focused on the product itself (i.e., alcohol, as opposed to aspects of the wider environment).

Study Site

This study will be administered by the School of Psychological Science at the University of Bristol, but will be conducted in bars and public houses in the UK.

Recruitment

Sites will be recruited by directly contacting publicans. We will initially use existing contacts who took part in at least one of our previous alcohol field studies (i.e., glass shape field study and / or serving size field study) and expressed an interest in taking part in future studies. Sites will be offered financial compensation of £500 for participating in this study.

Inclusion criteria for pubs and bars

- Have at least three alcoholic beers (lager or ale) on draught.
- Do not currently have any alcohol-free beers (lager or ale) on draught to ensure that the intervention (i.e., introducing alcohol-free beer on draught) is novel for all sites.
- Willing to remove one draught alcoholic beer and replace it with one draught alcohol-free beer.
- Have an electronic point of sale (EPOS) till system to record itemised sales of all drinks.
- Be willing to update the EPOS system to include ‘draught alcohol-free beer’ during intervention periods.
- Be willing to share itemised EPOS data with the research team for the duration of the study.
- Be willing to advertise the new draught beer in the same way the pub or bar would with any other new product (tap badges, signs behind the bar and information on menus and any apps).

Withdrawal of sites

Sites will be informed that they are free to withdraw from the study at any time. In the event that a site withdraws during data collection, they will not receive any financial reimbursement.

Sites will be able to withdraw complete data up to one year after the study or until the data are made open for sharing (whichever comes first) without having to give a reason.

Precision estimate

We previously conducted a field study in 24 sites in the UK to estimate the impact on alcohol consumption of serving draught alcoholic beer in straight-sided glasses compared with usual, predominantly curved glasses (Brocklebank *et al.*, 2021). This study had a similar design to the current study and found a mean difference of -35 litres in the volume of draught alcoholic beer sold between intervention and control periods (A-B). The standard deviation (SD) of this mean difference was 141 litres. Table 1 reports the 95% confidence interval (CI) of this SD for increasing values of N. Table 1 suggests that a minimum of 12 and up to 16 sites are required to have sufficient precision in the current study because it is at this point that the relationship between increasing N and increasing precision (i.e., narrower 95% CI of the SD) starts to plateau.

Table 1. Precision estimate: calculating the 95% CI of the SD

SD (litres)	N	Lower CI (litres)	Upper CI (litres)
141	6	88	346
141	8	93	288
141	10	97	258
141	12	100	240
141	14	102	228
141	16	104	219
141	18	106	212
141	20	107	206
141	22	109	202
141	24	110	198

N = the number of bars and public houses.

We consider this to be an opportunistic study providing preliminary evidence to inform future research, including more precise calculation of the likely effect size and the required sample size for future studies.

Randomisation

The random order for the four periods (two intervention and two control periods) will be generated at the start of the study using a computer-generated list of random numbers. This list will be produced by computer by an independent researcher who will email a member of the research team the order allocations in separate files (one for each of the participating sites). After a site has been recruited and eligibility has been confirmed, the password-protected file relating to that enrolment number will be opened by a member of the research team and the site will be allocated to one of four possible orders: 1) BABA; 2) BAAB; 3) ABBA; or 4) ABAB. Blocked randomisation will be used to ensure that an equal number of sites are assigned to each order (Figure 1).

It is not possible to blind the research team or the participating sites to order allocation. Drinkers will however not be aware of the study and therefore will be blinded to the study hypothesis.

[figure not shown]

Figure 1. Random order allocation.

All participating sites will perform two intervention periods (A) and two control periods (B) in a random order. Each period will last two weeks. During the intervention condition, sites will remove one draught alcoholic beer and replace it with one draught alcohol-free beer (i.e., increased proportion). During the control condition, sites will have no alcohol-free beer on draught (i.e., none).

Measures

Primary outcome

The mean volume (in litres) of draught alcoholic beer (lager and ale combined) sold weekly. This will be an aggregated value of the two two-week A periods and the two two-week B periods, respectively, expressed as a weekly amount.

Secondary outcome

Mean weekly revenue from all drinks (in £) (i.e., alcoholic and alcohol-free drinks combined).

Tertiary outcomes

1. The mean volume (in litres) of all alcohol-free beer (i.e., lager and ale combined) sold weekly, including both draught and bottled.

2. The mean volume (in litres) of all alcoholic beer (i.e., lager and ale combined) sold weekly, including both draught and bottled.
3. The mean volume (in litres) of bottled alcoholic beer (i.e., lager and ale combined) sold weekly.
4. The mean volume (in litres) of all alcoholic drinks sold weekly, excluding alcoholic beer.
5. The mean volume (in litres) of all alcohol-free drinks sold weekly, excluding alcohol-free beer and soft drinks.
6. The mean number of soft drinks sold weekly.

All outcomes will be aggregated values of the two two-week A periods and the two two-week B periods, respectively, expressed as a weekly amount.

Additional measures

1. The total number of non-study drinks (i.e., not including any draught alcohol-free beer sold) sold weekly will be used as a proxy measure of site busyness.
2. The total number of special events during each period that were likely to have increased sales. Special events will include any event held by the site that is outside of the normal schedule for that site. Therefore, this will exclude any regular events (i.e., weekly, fortnightly and monthly events), but will include any public holidays or sporting events.
3. The total number of alcohol-free drink options at baseline (i.e., during usual practice).

Procedures

This protocol will be pre-registered on the Open Science Framework.

We anticipate that all data will be collected between July 2022 and 21st November 2022 (therefore, data collection at each site will commence before the 25th Sept 2022). If data collection needs to continue past this time point, the study will be paused between 21st November 2022 and February 1st 2023 to allow for the FIFA world cup, Christmas period and Dry January period.

Written consent will be obtained for each site prior to data collection.

Sites will change the proportion of draught alcohol-free beer two to four times over a period of eight weeks depending on random order allocation (Figure 1). During each intervention period EPOS systems will be updated as appropriate to reflect the new draught alcohol-free beer option. Site leads will be provided with a schedule and contacted 24-hours before each reversal to remind them of the required changes. At the end of the study, all data will be sent electronically by each site to the research team. Once the data has been received by the research team the site will receive reimbursement.

During both study periods sites will still be able to sell alcohol-free beer in bottles or cans. Prior to publication, results will be shared with the site leads by email or face-to-face and they will be invited to comment.

Fidelity Checks

Fidelity to the protocol will be checked by site visits organised by the research team in the first few days after each reversal.

A site will be considered to have failed the fidelity check if any of the following criteria are **not** satisfied:

Intervention (A) periods

- One draught alcoholic beer has been removed and replaced with one draught alcohol-free beer.
- A confederate for the research team will order a pint / half pint of draught alcohol-free beer. Compliance with the intervention would require bar staff to serve a pint / half pint of draught alcohol-free beer.
- A confederate will observe the site for a period of 30 minutes. Compliance with the intervention would require that customers ordering a pint / half pint of draught alcohol-free beer are being served a pint / half pint of draught-alcohol free beer.

Any promotion of the draught alcohol-free beer through tap badges, information on menus and apps, and signs behind the bar, will be recorded. However, a lack of any of these promotions will **not** result in a fidelity check fail.

Control (B) periods

- There are no draught alcohol-free beers being sold.
- A confederate will order a pint / half pint of draught alcohol-free beer. Compliance with the intervention would require bar staff not to serve a pint / half pint of draught alcohol-free beer.
- A confederate will observe the site for a period of 30 minutes. Compliance with the intervention would require that customers ordering a pint / half pint of draught alcohol-free beer are not being served a pint / half pint of draught-alcohol free beer.

If a site fails any of the checks, they will be asked to rectify the observed protocol violation before an additional fidelity check takes place within 24 hours. A site might be asked to extend the study period to make up for days that have to be excluded from the analyses due to failed fidelity checks. However, sites will not be excluded if they fail ≥ 1 attention check and will still receive full reimbursement.

Site leads and staff will issue a simple explanation to patrons who ask why the draught beer options have changed: “We have been receiving requests for alcohol-free beer on draught, so we are trying out some changes for a few months”.

Site leads will be invited to take part in a 30-minute end-of-study interview after the final study period to answer questions about their experience of taking part and for any verbal feedback they receive from patrons during the study period. This will take place by telephone or face-to-face.

Statistical Plan

Primary outcome

Primary analysis: For the primary analysis of the primary outcome the mean difference will be estimated according to whether alcohol-free draught was available or not available. This will be done by comparing the mean volume (in litres) of draught alcoholic beer (lager and ale combined) sold weekly between the A periods and the B periods using a mixed effects model for repeated measures, or similar (i.e., availability of alcohol-free draught beer compared to no availability of alcohol-free draught beer).

Unadjusted mean differences with 95% CIs, t statistic and p values will be reported. A Cohen's d effect size will also be calculated.

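### The control-period fidelity check does not test whether the removed alcoholic beer is back on tap, so a site with an idle line would count as compliant

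*Protocol*

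**What the plan says.** Under Study Aim and Hypotheses, the first hypothesis is "Replacing one draught alcoholic beer with one draught alcohol-free beer lowers the volume of draught alcoholic beer sold in licensed premises". Study Design describes control as follows: "During the control condition, sites will have no alcohol-free beer on draught (i.e., usual practice". The Randomisation section repeats it without mentioning usual practice: "During the control condition, sites will have no alcohol-free beer on draught (i.e., none". The sequences are "1) BABA; 2) BAAB; 3) ABBA; or 4) ABAB".

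Under Fidelity Checks, the timing is "Fidelity to the protocol will be checked by site visits organised by the research team in the first few days after each reversal". The first A-period criterion is "One draught alcoholic beer has been removed and replaced with one draught alcohol-free beer". The first B-period criterion is "There are no draught alcohol-free beers being sold". The second concerns a confederate's order: "Compliance with the intervention would require bar staff not to serve a pint / half pint of draught alcohol-free beer". The third is a 30-minute observation that customers are not served alcohol-free draught.

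A failed check leads to a request to rectify and a repeat check within 24 hours. Days may be excluded and the study period extended. Under Sensitivity analysis, the per-protocol analysis drops sites with at least one failed check. The Intervention section records beer type for both the removed and the replacement beer, but brand only for the replacement.

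**The concern.** A crossover with reversals relies on each control period being a genuine return to baseline. Here the return has two parts: the alcohol-free beer goes off and the removed alcoholic beer comes back. The B criteria test only the first part. A site that takes the alcohol-free keg off and leaves the line empty meets all three, although it is not at usual practice.

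The primary outcome is litres of draught alcoholic beer, so the number of alcoholic lines on sale in B bears on it directly. The per-protocol analysis is the planned protection against poor adherence. It would not help, because membership depends on the same checks. Revenue is also exposed: an idle line could lower control revenue and make the swap look harmless to takings when it is not.

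**Working it through.** **1. The criteria side by side**

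| Element of the swap | Tested in A? | Tested in B? |
|---|---|---|
| Alcohol-free draught present (A) or absent (B) | Yes | Yes, by all three criteria |
| Alcoholic beer removed (A) or restored (B) | Yes, first criterion | No |

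The rule in the Intervention section that replacements stay consistent governs the pair of beers used. It is not a B-period check.

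**2. The plan's own count of changes.** Procedures gives two to four changes per site. Counting a change whenever the taps differ from the preceding state, and starting from usual practice: BABA 3, BAAB 2, ABBA 3, ABAB 4. The range is reproduced.

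**3. Which B periods are exposed.** Each sequence has two B periods, so there are 8.

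| Sequence | B periods | After an A period | Followed by a later A period |
|---|---|---|---|
| BABA | 1, 3 | 3 | 3 |
| BAAB | 1, 4 | 4 | none |
| ABBA | 2, 3 | 2, 3 | 2, 3 |
| ABAB | 2, 4 | 2, 4 | 2 |

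Exposed: 1 + 1 + 2 + 2 = 6 of 8. For 1 + 0 + 2 + 1 = 4 of these, a later A-period visit might bring the problem to light. For the final B of BAAB and of ABAB there is no later A visit.

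**4. What A−B estimates with an idle line.** Let S(k, a) be weekly litres of draught alcoholic beer with k alcoholic lines and a alcohol-free lines. The planned contrast splits into two parts:

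S(k−1, 1) − S(k, 0) = [S(k−1, 1) − S(k−1, 0)] + [S(k−1, 0) − S(k, 0)] = D_add + D_remove.

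With an idle line in B, the control value is S(k−1, 0), so only D_add remains. At the smallest eligible site (three alcoholic draught beers), the comparison of alcoholic lines in B against A changes from 3 versus 2 to 2 versus 2.

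If a fraction f of control site-periods is affected, and sites contribute equally:

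expected A−B = D_add + (1 − f) × D_remove.

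If D_remove is 0, nothing changes. If D_remove is negative and D_add is not positive, the estimate moves towards zero by f × |D_remove|.

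**5. Illustration only.** The documents give neither f nor D_remove. Borrow the −35 litres that Precision estimate reports from the earlier glass-shape study, and assume that all of it is D_remove. Then expected A−B = −35 × (1 − f). Twelve sites give 12 × 2 = 24 control site-periods.

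- f = 1/24 (one site-period): −33.5 litres
- f = 1/12 (two site-periods): −32.1 litres
- f = 0.25: −26.25 litres
- f = 0.50: −17.5 litres

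With equal allocation f cannot exceed 6/8 = 0.75, so f = 0.25 already means that 0.25/0.75 = one third of exposed periods fail.

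For scale, take the stated SD of 141 litres as the SD of site differences. The 95% half-width at 12 sites is 2.201 × 141/√12 = 89.6 litres. One or two affected site-periods would shift the estimate by 1.5 to 2.9 litres, which is small beside that.

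**The case against.** The strongest reply is that restoration is already required and only its verification is missing. Usual practice obliges a site to return to its normal range. Site leads receive a schedule and a reminder 24 hours before each reversal, and an idle line costs the publican sales. The Statistical Plan also describes the primary contrast as alcohol-free draught available against not available, and the B checks test exactly that. All of this stands. It makes the failure less likely, but the stated pass/fail rule would still classify it as compliance.

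A later A-period visit may reveal an unrestored line at four of the six exposed periods. That is possible but weak protection, because the taps look the same in A whether or not the beer came back in between.

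Three stronger readings are tempting, and the documents do not support them:

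- A reader might infer that a guest beer in the line does the same harm. It does not. The number of alcoholic lines stays at its usual level, so the argument in step 4 does not apply. It is still not usual practice, and the direction of its effect is uncertain.
- A reader might note that visits follow reversals only, so 4 of the 16 sequence-periods (25%) go unvisited, and count them all against restoration. Two are first-period B (BABA, BAAB), before anything has been removed, and one is an A period (BAAB, third). Only the third period of ABBA concerns restoration, and it continues a B period that was visited.
- A reader might treat bias towards zero as established. It depends on the lost line lowering sales. If drinkers simply move to another alcoholic tap, an idle line changes little.

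The SAP, which is not shown, may tabulate compliance from till data. The fidelity criteria themselves are fixed in the Protocol, so the gap in them is a fair point.

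**Conclusion.** The point holds as a gap in the stated compliance rule. The A check tests both halves of the swap and the B check tests one, so a site with an idle line in a B period after an A period passes, is not asked to rectify, and stays in the per-protocol set. Six of 8 B sequence-periods offer the opportunity, two of them with no later A visit. This counts exposure, not occurrence.

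A reader might conclude that the trial does not compare the swap at all. The documents do not support that: the contrast changes only at sites that fail to restore the beer, and the plan intends that they do. Where it happens, A−B estimates the addition of an alcohol-free line. Provided the lost line itself lowers sales and revenue, the primary estimate is pulled towards zero and the hypothesis of no revenue reduction is favoured. The failure rate and the lost-line effect are both unknown, so the litre figures above are illustrations. This is a worthwhile, inexpensive improvement and not a flaw that invalidates the design.

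**What to change.** - Record at enrolment the identity (brand and product) of the alcoholic beer to be removed, and the baseline number of draught alcoholic beers. At present only the removed beer's type is recorded, so a check that the same beer has returned has nothing to refer to.
- Add a fourth B-period criterion for periods after an A period: the draught alcoholic beer removed in the A period is back on sale, and the number of draught alcoholic beers equals baseline. Check it at the visits already planned, with the same consequences as any other failed criterion.
- Confirm it for each period, including the unvisited third period of ABBA, from the itemised till data that sites already agree to share. Set a tolerance in advance for isolated mis-keyed entries. A strict zero-sales rule could fail a site on one till error, and the per-protocol analysis drops whole sites from only 12 to 16.

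The cost is one or two extra recorded items, one line on the fidelity form and one tabulation, with no extra visits. The downside is that a few more sites may be classed as non-compliant in the per-protocol analysis.
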